Hypothesis 1.1: Bladder instillation with a gentamicin antimicrobial solution will result in significantly decreased episodes of symptomatic UTIs, fewer courses of oral antibiotics, and a reduction of multi-drug resistant organisms on urine culture, as compared to controls.

Hypothesis 1.2: Bladder instillation with a gentamicin antimicrobial solution will decrease detrusor spasms, increase bladder compliance as well as mitigate the rapid rise in systolic blood pressure (autonomic dysreflexia) evidenced during cystometry as compared to controls.

B. Study Design/Methodology

In a randomized, double-blind, prospective study, we will compare the long-term effects (80 daily sessions, 2x per day) of a bladder instillation protocol in 3 groups of individuals (n=36; 3 groups of 12) with chronic SCI receiving either:

1) gentamicin bladder instillation

2) saline installation

3) no instillation (catheter clamping only in those with suprapubic catheters for the duration of the irrigation time frame - refer to Fig. 2 timeline).

The control groups will also serve to address the question of whether bacteria already colonized in the bladder would also provide a protective role in preventing more pathogenic bacteria or other organisms, such as yeast, which also colonize the bladder. Research participants will complete the 80 sessions of twice per day instillations initially in the Urogenital and Bowel Laboratory, where blood pressure and heart rate will be continually monitored (approximately 1-2 weeks). Once safe pressures are established, the remaining instillations may be completed in the home setting. A major issue confounding validity of a clinical trial is compliance. Given that this study assesses the long-term outcomes of daily bladder instillations and allows for the twice-daily instillations to be conducted in the home-setting, it is possible that participants may not be fully

compliant with respect to study duration and frequency of instillations. In an effort to improve the applicability of the study results to individual participants and mitigate non-compliance, our research nurse will guide participants through all aspects of the instillation procedure to ensure that they are fully independent. At-home blood pressure monitoring during instillation times is automatically recorded and will be an additional step in monitoring protocol adherence.

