
The following participant withdrawal criteria may be implemented in determining when and how to withdraw participants from the trial/investigational product treatment.

Drug Discontinuation Criteria:

The subject's participation may be terminated for safety precautions based on any of the following by the study investigator. 1) Drug-related severe adverse event; 2) UTI requiring intravenous antibiotics; 3) Diagnosis of systemic absorption; 4) Diagnosis of nephrotoxicity; 5) Diagnosis of ototoxicity; 6) Diagnosis of renal failure

Temporary Discontinuation Criteria:

Situations of temporary discontinuation of study drug followed by subsequent resumption of study drug are: 1) Resolution of an adverse event, especially in cases where it is determined that the study drug was unlikely to have caused the event. 2) Resolution of a symptomatic UTI.

Withdrawal from Study:

A participant may withdraw from study participation at any time. Whatever data has been collected at the time of study termination will be evaluated by the PI for use in the final study database. If a participant is terminated from the study, the investigator will have the option to recruit an additional participant. Of withdraw from the study was due to an adverse event, participants will be followed until complete resolution of the adverse event that was possibly or definitely drug-related.

2. Statistical Plan: Data will first be summarized. We will use means with associated standard deviation, median with associated interquartile range and full range (min-max) to summarize continuous variables. Categorical variables will be summarized with frequency count and standard deviation. We will perform 2 types of analyses: pre-post differences within each group and between group comparisons of the differences. To evaluate the pre-post changes in each group, we will use paired t-test. To compare the changes between the 3 groups, we will use ANOVA test. If the ANOVA test yields significant results, we will perform follow-up 2 by 2 group comparisons using 2-sample t-tests. If the underlying assumptions of these tests are not satisfied, we will use the non-parametric equivalent tests instead.

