We propose to use a sample size of 36 (12 in each of the three arms). Cox et al., (46) has found that the use of intravesical gentamicin was associated with a reduction of a median 3 symptomatic UTIs in 6 months in 22 patients. Using the formulas proposed by Hozo et al., (47) we estimated the corresponding standard mean change to be 2.48 with a standard deviation of 1.7. Assuming the same standard deviation in our data, a sample size of 12 achieves 80% power to detect a mean of paired differences of as low as 1.5 symptomatic UTIs for the gentamicin group with a significance level of 0.05 using a two-sided paired ttest (48, 49). We expect to observe a drop of at least 2 symptomatic UTIs in 6 months. With the same setting, i.e. SD = 1.7, a sample size of 12 achieves 97% power to detect that. Our study will compare changes between the gentamicin instillation, the saline instillation and the no-instillation groups. We will use the comparison between the gentamicin and the non-instillation group to estimate the power. The estimated effect of gentamicin is a reduction in symptomatic UTIs of 2 with a standard deviation of 1.7 (described above) and we assume no change for the non-instillation group (mean reduction of 0 with a standard deviation of 0). With these values, sample sizes of 12 (gentamicin) and 12 (no-instillation) achieve 96% power to reject the null hypothesis of equal means with a significance level of 0.050 using a two-sided two-sample unequal-variance t-test (48-51). The power analysis was performed in PASS 14 Power Analysis and Sample Size Software (NCSS, LLC. Kaysville, Utah, USA, ncss.com/software/pass).

Experimental Outcomes – Research Procedures

1. Intravesical Gentamicin Sulfate Instillation

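### Symptomatic UTI counts are compared as unadjusted pre-post changes, with no baseline adjustment, no days at risk and no rule for early leavers; this loses power and leaves room for bias if leaving differs by arm

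*Combined protocol and SAP*

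**What the plan says.** Hypothesis 1.1 (section II.A) expects "significantly decreased episodes of symptomatic UTIs, fewer courses of oral antibiotics" with gentamicin, so the outcome is a count of episodes. Section II.B.2 analyses it in three steps. Within each arm: "To evaluate the pre-post changes in each group, we will use paired t-test". Between arms: "To compare the changes between the 3 groups, we will use ANOVA test". If that is significant, "we will perform follow-up 2 by 2 group comparisons using 2-sample t-tests". The fallback reads "If the underlying assumptions of these tests are not satisfied, we will use the non-parametric equivalent tests instead". No baseline covariate, rate, person-time, offset or count model appears anywhere.

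The periods behind the change are not defined. Entry uses UTI history over 6 or 12 months (section III, Inclusion Criteria), the intervention lasts 80 days (section III.A), and the power text speaks of 6 months.

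Participation may be ended for, among other reasons, a UTI needing intravenous antibiotics, nephrotoxicity or ototoxicity (section II.B.1, Drug Discontinuation Criteria). For those who leave, "Whatever data has been collected at the time of study termination will be evaluated by the PI" for possible use in the final database, and an additional participant may be recruited. No analysis rule follows.

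**The concern.** Two things can go wrong with this analysis of a small count.

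First, precision. At 4 UTIs per 6 months (an assumption), a control would have about 1.75 UTIs in 80 days. Subtracting a historical count that is itself subject to chance adds that noise to the comparison. A regression on baseline uses the same information without that penalty.

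Second, time at risk. A raw count from someone observed for a few weeks is not comparable with one from someone observed for 80 days. Neither the t-test, ANOVA nor rank tests on the same changes use days observed. This matters when early leaving differs by arm, and the discontinuation criteria make that plausible in either direction: severe UTIs may shorten observation in the control arms, and drug toxicity may shorten it on gentamicin. At stake are the power for the effect the trial hopes to see and, with unequal leaving, the size of the estimated effect.

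**Working it through.** **1. The plan's own power figures.** Section II.B.2 uses n = 12 and SD 1.7, "with a significance level of 0.05 using a two-sided paired ttest". The standard error is 1.7/√12 = 0.491 on 11 df. By the noncentral t:
- Paired, change 1.5 (1.5/0.491 = 3.06): 79.4% (stated 80%).
- Paired, change 2 (2/0.491 = 4.08): 95.9% (stated 97%).
- Two-sample, 2 v 0 with SDs 1.7 and 0 (same ratio and df): 95.9% (stated 96%).

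These reproduce within 2 points. The last one relies on a control SD of 0; with SD 1.7 in both arms it is 78.6%.

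**2. How small the counts are.** 80 days is 80/182.5 = 0.438 of 6 months. At an assumed 4 per 6 months, controls expect 4 × 0.438 = 1.75 UTIs (17% with none), and half that rate gives 0.88 (42% with none). At 2 per 6 months the figures are 0.88 and 0.44. The plan hopes for a drop of 2 per 6 months. From a base of 3 or 4 that is a rate ratio of 1/3 = 0.33 or 2/4 = 0.5.

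**3. Why subtraction costs power.** Take 4 per 6 months, rate ratio 0.33 and between-person variance 0.1 on the relative-rate scale, ignoring the entry rule and early leaving. Baseline is scaled to 80 days, so its Poisson variance is 0.438² × 4 = 0.192 × 4 = 0.77. The expected difference is 1.75 × 0.67 = 1.17.
- Variance of change: controls 1.75 + 0.77 = 2.52; gentamicin 0.58 + 0.77 + 0.1 × 1.17² = 1.49. SE = √((2.52 + 1.49)/12) = 0.578; 1.17/0.578 = 2.03; power about 49%.
- Variance of the on-study count alone: controls 1.75 + 0.1 × 1.75² = 2.06; gentamicin 0.58 + 0.1 × 0.58² = 0.61. SE = √((2.06 + 0.61)/12) = 0.472; 1.17/0.472 = 2.48; power about 65%.

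In this setting, subtracting the baseline is worse than ignoring it.

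**4. Simulation.** Assumptions not in the documents: gamma-Poisson counts, mean 3-4 UTIs per 6 months before an entry rule of at least 2, dispersion 0.1 or 0.3, 15% leaving early at random in both arms, 12 v 12, 80 days. The rate model is quasi-Poisson with log baseline and log-time offset.

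| Rate ratio 0.33 | Power |
|---|---|
| Change-score t-test | 40-51% |
| Rank test on change | 39-47% |
| Rate model | 44-61% |
| ANCOVA on raw count with baseline | 51-65% |

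At rate ratio 0.5 the gain over the t-test is about 4-10 points for ANCOVA and about -3 to 5 points for the rate model. Correcting the change score for time observed, without baseline adjustment, adds only about 1-3 points at 0.33. Most of the loss therefore comes from the change score.

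**5. Leaving that differs by arm.** Suppose 30% of one arm leave, on average half-way, and raw counts are kept. The false difference is 4 × 0.3 × 0.5 = 0.6 UTI per 6 months, or 1.75 × 0.3 × 0.5 = 0.26 over 80 days.
- No true effect, 80 days: t-test type I error about 6-7%.
- Controls leaving, rate ratio 0.33, 80 days: t-test 37%, ANCOVA on raw counts 48%, offset model 61%.
- If instead the gentamicin arm leaves more, the benefit is overstated.

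Here ANCOVA on raw counts is not enough and the offset matters. Leaving was simulated at random within arm; stopping triggered by a UTI was not simulated.

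**The case against.** The strongest reply is that this is a feasibility study with a generic plan that also serves urodynamic and laboratory outcomes, and that the change-score t-test is valid: with full or balanced follow-up its simulated type I error is about 4-6%. That stands. So does the point that a plain linear model with baseline and no offset does at least as well as the rate model when leaving is balanced. The case for the offset therefore rests on unequal leaving.

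Four stronger readings are tempting, and the material does not support them.
- A reader might infer that early leavers are counted as if fully followed. The plan does not say so: their data are left to the investigator's evaluation and they may be replaced, so exclusion is equally possible. The gap is the missing rule.
- A reader might infer that temporary discontinuation shortens follow-up. It pauses study drug; nothing says that observation ends.
- A reader might infer that the rank fallback is much worse. It is 0-4 points below the t-test, close to simulation error.
- A reader might infer that a count model restores adequate power. It does not at rate ratios of 0.33 or 0.5.

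**Conclusion.** The point holds as a matter of efficiency and of an undefined rule, not as an invalid test. Under the assumed rates, unadjusted change scores cost about 11-14 points of power at rate ratio 0.33 compared with baseline adjustment (40-51% against 51-65%), and less at 0.5. Bias is conditional: it needs leaving that differs by arm with raw counts kept, or outcome-related exclusion if leavers are dropped. The discontinuation criteria make either plausible, but the documents give no leaving rates, so the 15% and 30% used here are illustrations. The sizes rest on the assumed UTI rates, dispersion and 80-day window. A change is worth making, with medium confidence in its size.

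**What to change.** For symptomatic UTIs, replace the change-score tests in section II.B.2 with the following, fixed before unblinding:
- **Outcome and population:** the on-study UTI count for all randomised participants, each for the days actually observed, including periods off study drug. State how leavers and additional recruits enter the analysis, rather than leaving this to case-by-case evaluation.
- **Model:** quasi-Poisson or negative binomial regression on arm, with log days at risk as offset, baseline UTI rate and catheter type as covariates. Report rate ratios with 95% CIs and a permutation p-value as a small-sample check.
- **Baseline:** one fixed pre-study window. Twelve months works because both entry routes (3 in a year, or 2 in 6 months) guarantee a count above zero. On a 6-month window someone admitted on the yearly criterion may have none, so log(count + 0.5) would be needed.
- **Windows:** reconcile the 6- or 12-month history, the 80 days and the 6 months of the power text.

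The cost is mostly analysis wording, plus collecting one baseline count over the chosen window; UTI history is already needed for entry. The downside is a model assumption with few participants, which the permutation check addresses. An offset corrects for time observed but not fully for stopping that a UTI itself triggers, so reasons for leaving should be reported by arm. The protocol should also acknowledge that power remains below 80% at 12 per arm under these assumptions.

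### The stated 96% is the power of a stand-alone t-test; for the planned ANOVA-then-t-test sequence it is an upper bound and depends on saline-arm values the plan does not give

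*Combined protocol and SAP*

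**What the plan says.** All the relevant text is in the Statistical Plan (section II.B, item 2).

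- Between-group analysis: "To compare the changes between the 3 groups, we will use ANOVA test".
- Pairwise comparisons are conditional on that result: "If the ANOVA test yields significant results, we will perform follow-up 2 by 2 group comparisons using 2-sample t-tests". The text does not say whether these t-tests pool the variances.
- Fallback: "If the underlying assumptions of these tests are not satisfied, we will use the non-parametric equivalent tests instead".
- Size: "We propose to use a sample size of 36 (12 in each of the three arms").
- Power is worked out for one pair of arms: "We will use the comparison between the gentamicin and the non-instillation group to estimate the power". The inputs are "The estimated effect of gentamicin is a reduction in symptomatic UTIs of 2 with a standard deviation of 1.7" for gentamicin and, for the control, "we assume no change for the non-instillation group (mean reduction of 0 with a standard deviation of 0").
- Result: 12 versus 12 "achieve 96% power to reject the null hypothesis of equal means with a significance level of 0.050 using a two-sided two-sample unequal-variance t-test".

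No mean or SD is given for the saline arm. No power is given for the ANOVA, or for the ANOVA followed by a pairwise test.

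**The concern.** The only between-group power figure belongs to a test that the plan does not run on its own. Gentamicin is compared with no instillation only if the three-group ANOVA is significant first. Success therefore needs two rejections, and the probability of both cannot exceed the probability of the second alone.

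The first step also depends on the saline arm. Its mean affects the spread between groups, and its variance enters the ANOVA error term. The power calculation uses neither. Hypothesis 1.1 sets gentamicin against controls. If the ANOVA misses significance because of how the saline arm behaves, a gentamicin effect that the powered t-test would have detected gets no between-group test. With 12 per arm there may be little power to spare.

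**Working it through.** **Inputs from the Statistical Plan.** 12 per arm; gentamicin mean reduction 2, SD 1.7; no instillation mean 0, SD 0; two-sided 0.05; unequal-variance t-test.

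**Assumptions added here.** Saline mean reduction from 0 to 2 and saline SD from 0 to 1.7; normally distributed changes; ordinary one-way ANOVA at 0.05; unequal-variance t-test at the second step.

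**Step 1: reproduce the stated figure.** With SDs 1.7 and 0, the standard error is 1.7/√12 = 0.491. The noncentrality is 2/0.491 = 4.075, with 11 df and critical t = 2.201. Power from the noncentral t is 95.9%. The stated 96% is right for the stand-alone test.

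**Step 2: the gate when both control SDs are 0.** Let m and V be the gentamicin sample mean and variance, and s the saline mean.

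- t-test: t² = 12m²/V, which must exceed 2.201² = 4.844.
- ANOVA within mean square: (V + 0 + 0)/3 = V/3.
- ANOVA between mean square: 12 × the sample variance of (m, s, 0). This is smallest at s = m/2, where it is 12 × m²/4 = 3m².
- So F is at least 3m²/(V/3) = 9m²/V = 0.75t².

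Whenever the t-test rejects, F is at least 0.75 × 4.844 = 3.633, above the critical value 3.285 (2 and 33 df). Every t-test rejection therefore passes the gate, and power stays at 95.9% for any saline mean.

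**Step 3: the gate when saline varies.** The table gives the simulated probability (%) that both the ANOVA and the t-test reject, from 400,000 trials per cell (Monte Carlo standard error below 0.1 point).

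| SD: no instillation / saline | Saline 0 | 0.5 | 1 | 1.5 | 2 |
|---|---|---|---|---|---|
| 0 / 0 | 95.9 | 95.9 | 95.9 | 95.9 | 95.9 |
| 0 / 0.5 | 95.9 | 95.9 | 95.9 | 95.9 | 95.9 |
| 0 / 1.0 | 95.5 | 94.7 | 95.1 | 95.9 | 95.9 |
| 0 / 1.5 | 93.3 | 91.2 | 91.7 | 94.1 | 95.6 |
| 0 / 1.7 | 91.7 | 88.8 | 89.3 | 92.5 | 95.0 |
| 1.7 / 1.7 | 74.1 | 69.8 | 67.8 | 69.8 | 73.9 |

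**Step 4: split the fall in the last row.** With SD 1.7 in all arms, the stand-alone unequal-variance test has 78% power. Replacing SD 0 by 1.7 therefore costs about 96 − 78 = 18 points. The gate takes a further 78.5 − 74.1 = 4.4 points at saline change 0, and 78.3 − 67.8 = 10.5 at saline change 1: roughly 4 to 10 points.

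**Step 5: the non-parametric fallback.** Kruskal-Wallis followed by Mann-Whitney (3,000 trials per scenario, so less precise) gives about 96% with both control SDs 0. It gives 90% with saline SD 1.7 and saline change 0, and 63-69% with SD 1.7 in all arms. The pattern is the same.

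**The case against.** A reader might infer that the gate by itself means the planned procedure lacks 96% power. The documents do not support that. The only control variability they assume is 0. If saline is treated the same way, Step 2 shows that the gate costs nothing. With no-instillation SD 0, the loss is still nil at saline SD 0.5 and about 1 point at most at 1.0. A loss clearly above 2 points needs a saline SD of roughly 1.2 to 1.5 or more, and the plan gives no such value. The 89-95% figures are therefore not on the plan's own SDs; they add an assumed saline SD. That objection stands.

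Other points in the plan's favour also stand in part:

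- The text says openly that one comparison was used to estimate power, and the Objectives call this a feasibility study.
- The within-group paired t-test is not gated and has its own power statement (80% for a mean change of 1.5, 97% for 2).
- The type of ANOVA and of follow-up t-test is not specified. If the follow-up pooled the variances, simulated stand-alone power on the plan's SDs would be 97%. The upper bound of 96% belongs to the unequal-variance test that was powered.

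It is also tempting to say that the gate should go. An ANOVA followed by pairwise tests is a recognised approach for three groups, and the alternatives do not reliably gain power. Holm-adjusted gentamicin-versus-control contrasts give 91-92% with both control SDs 0 (against 96% gated) and 68-74% with SD 1.7 throughout. A Welch ANOVA gate gives 66-73% in the latter case, and its weights are undefined at an SD of 0.

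None of this answers the central point: the reported power is for a different procedure from the one planned.

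**Conclusion.** The point holds in a limited form. The 96% is correct for a stand-alone unequal-variance t-test of gentamicin versus no instillation. For the planned sequence it is an upper bound that has not been shown to be attained, because the answer turns on a saline mean and SD that the plan omits.

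Accepting SD 0 for no instillation, the true figure lies between no loss (saline SD up to 0.5) and a loss of about 1 to 7 points (saline SD 1.7, saline change 0 to 2). With SD 1.7 in all arms the sequence has 68-74% power. Most of that shortfall comes from the SD-0 assumption, a separate weakness, and only about 4 to 10 points from the gate. Correcting the control SD alone would still leave power reported for the wrong procedure.

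These figures assume normal changes, 12 analysed per arm and an ordinary ANOVA. The saline values are assumptions, and 1.7 is used because it is the only non-zero SD of change in the plan.

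**What to change.** In the sample-size paragraph of the Statistical Plan, state the assumed saline mean and SD. Restate the between-group power as the probability that the ANOVA and then the gentamicin versus no-instillation t-test are both significant. Show it over a range of saline means, saline SDs and non-zero control SDs, and say which form of t-test follows the ANOVA. The present 96% can stay if it is labelled as the stand-alone figure.

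Replacing the gate with Holm-adjusted contrasts or a Welch ANOVA is a matter of preference and is not required.

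The cost is a few sentences, a short simulation and probably a less favourable number. No study procedure changes. The restated figure may raise the question of size: with SD 1.7 in all arms, 80% power for the gated sequence needs about 14 to 16 per arm before dropout, depending on the saline mean.

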The potential research participant will be consented for participation and assessed for medical eligibility by the research team's Physiatrist, and/or Nurse Practitioner (as applicable). The Nurse Practitioner will conduct a medical history and physical examination and determine medical eligibility based on the clinical inclusion criteria and exclusion criteria and consideration of the risk assessment specific for the individual based on their medical history and examination. Following medical clearance for the assessments, the potential research participant will undergo urological assessments. Potential study eligibility will be determined by the investigators based on the evaluation of these assessments to be consistent with the inclusion criteria. The participant will then complete the bladder washout protocol for the study for 80 days and may continue with his/her current daily activities. Throughout the protocol, a number of assessments will be performed to assess the participant's progress in the study. Following the protocol, the participant will participate in post-instillation bladder assessments.

B. Consent and Eligibility Documentation

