Day-to-day oversight of the trial is provided by the Principal Investigators (PIs), Drs. [name] and [name]. They will review all study data and any adverse events, and report all adverse events to the Medical Monitor, sponsor, and University of Louisville IRB. Monitoring for the study will be provided by a Medical Monitor who will review study conduct including accrual, drop-outs, protocol deviations, and AEs in aggregate on an annual basis. The Medical Monitor will review serious adverse events (SAEs) in real-time. All data analyses (Labs, urodynamics, ultrasound) will be conducted as assessed with annual summary reports generated. Study data will be provided to the Medical Monitor to each annual review

one month prior. Data reports will be prepared by the principal investigators and the study statistician. The Medical Monitor will provide a written report to the study team with recommendations for study modification, study continuation/discontinuation as relevant. The study team is responsible for forwarding the report to the IRB.

Figure 2. Study Timeline.

Screening Phase		Intervention		Midpoint		Intervention			Post Intervention		
Assessments		Groups		Assessments		Groups			Assessments		
Labs	*Fxnl	Gent (n=12)	Saline (n=12)	None (n=12)	Labs	*Fxnl	Gent (n=12)	Saline (n=12)	None (n=12)	Labs	*Fxnl
UA Culture + Sensitivity	UDS US ~Intake forms	IC (n=6) 28.8 mg in 60 ml NS	IC (n=6) 60 ml NS	IC (n=6) No procedure	UA Culture + Sensitivity CBC CMP HCG	UDS US ~Intake forms	IC (n=6) 28.8 mg in 60 ml NS	IC (n=6) 60 ml NS	IC (n=6) No procedure SP (n=6) Catheter clamping for duration of instillation.	UA Culture + Sensitivity	UDS US ~Intake forms
CBC CMP HCG		SP (n=6) 28.8 mg in 60 ml NS	SP (n=6) 60 ml NS	SP (n=6) Catheter clamping for duration of instillation			SP (n=6) 28.8 mg in 60 ml NS	SP (n=6) 60 ml NS		CBC CMP HCG	
5 days		80 instillations - 7x/wk - 2x/d		5 days		80 instillations 7x/week – 2/d			5 days		

CBC, Complete Blood Count; CMP, Comprehensive Metabolic Panel; Gent, Gentamicin sulfate; IC, Intermittent Catheterization; Fxnl, Functional; HCG, Human Chorionic Gonadotropin (Pregnancy Test); NS, Normal Saline; SP, Suprapubic Catheter; UDS, Urodynamic Study; US, Ultrasound.

*The term "functional", abbreviated fxnl in this study, signifies an objective assessment of bladder functioning using urodynamic testing and ultrasound imaging.

IV. References

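### The sample size rests on a 6-month effect and SD, but about 80 treatment days are scheduled and the UTI counting windows are undefined, so the stated power is not shown to apply

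*Combined protocol and SAP*

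**What the plan says.** **Sample size (II.B.2 Statistical Plan).** The effect comes from a published series that reported "a reduction of a median 3 symptomatic UTIs in 6 months in 22 patients". The plan converts this to a mean change of 2.48 with an SD of 1.7. "Assuming the same standard deviation in our data", it then gives three power figures for 12 per arm at a two-sided 5% level:

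- 80% for a within-arm drop of 1.5 (paired t-test);
- 97% for a within-arm drop of 2, introduced by "We expect to observe a drop of at least 2 symptomatic UTIs in 6 months";
- 96% for gentamicin against no instillation (Welch test), with the control arm set at "mean reduction of 0 with a standard deviation of 0".

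**Duration.** Three places describe it:

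- II.B Study Design/Methodology: "80 daily sessions, 2x per day";
- III.A Screening and Enrollment: "The participant will then complete the bladder washout protocol for the study for 80 days";
- Figure 2: two intervention blocks, "80 instillations - 7x/wk - 2x/d" and "80 instillations 7x/week – 2/d", separated by a 5-day midpoint assessment and followed by a 5-day post-intervention assessment.

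**Analysis (II.B.2).** Changes from pre to post are tested within each arm and compared between arms. The period over which UTIs are counted before and after the start of treatment is not given. The one-year and 6-month look-backs in section III are entry criteria only.

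**The concern.** The number of UTIs a person can avoid depends on how long that person is observed. An effect and an SD that belong to 6 months do not carry over to a shorter window unless both are restated, and the plan restates neither. The three power figures are the only justification given for 12 per arm, and the objectives in II.A include a test of efficacy. If the real window is less than half of 6 months, the trial may be less well powered than its readers are told.

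The missing window definitions add a second exposure. If baseline is taken from a 6-month history and follow-up from a shorter period, the within-arm change partly measures the difference in period length.

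**Working it through.** **Inputs.** From II.B.2: n = 12 per arm, SD 1.7, drops of 1.5 and 2, source mean 2.48, two-sided alpha 0.05, control SD 0. From Figure 2: 80 instillations per block at 2 per day. Six months is taken as 365.25/2 = 182.625 days.

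**Method.** Power comes from the noncentral t distribution with noncentrality = drop / (SD/√12) and 11 degrees of freedom. With a control SD of 0, the Welch test has the same standard error and also 11 degrees of freedom, so the paired and between-arm figures coincide.

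**Step 1: the plan's own figures.** 1.7/√12 = 0.491.

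- Drop 1.5: 1.5/0.491 = 3.06, power 79.4% (stated 80%).
- Drop 2: 2/0.491 = 4.08, power 95.9% (stated 97% paired, 96% between arms).

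The figures reproduce to within about 1 point on the 6-month basis.

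**Step 2: the scheduled window.** 80/2 = 40 days per block, and 40 + 40 = 80 treatment days, which agrees with III.A. Adding 5 + 5 assessment days gives 90. The discontinuation criteria that precede II.B.2 allow pauses, and nothing says whether paused days are made up, so 90 is not a ceiling.

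**Step 3: rescale the drop (assumed linear in time).**

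- 80 days: 80/182.625 = 0.438, so 2 becomes 0.876.
- 90 days: 90/182.625 = 0.493, so 2 becomes 0.986.

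**Step 4: power for a drop of 2 per 6 months.** The documents give no SD for the shorter window, so a range is shown (f is the time factor from step 3).

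| SD assumption | SD, 80 d | Power, 80 d | SD, 90 d | Power, 90 d |
|---|---|---|---|---|
| Unchanged, 1.7 | 1.70 | 37% | 1.70 | 45% |
| Variance proportional to time, 1.7 × √f | 1.13 | 69% | 1.19 | 74% |
| Intermediate, 1.7 × f^0.75 | 0.92 | 85% | 1.00 | 87% |
| SD proportional to time, 1.7 × f | 0.74 | 96% | 0.84 | 96% |

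Example, second row at 80 days: 0.876/(1.125/√12) = 0.876/0.325 = 2.70, power 69.0%.

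Under the same second-row rule at 80 days, the drop of 1.5 has 46% paired power (stated 80%), and the source mean of 2.48 has 86%.

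**Step 5: other readings of the duration, drop of 2.**

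- 80 days per Figure 2 block (160 days, or 170 with assessments): the drop becomes 1.75 to 1.86. Power is 90% (160 days, SD 1.7) to 96%.
- 80 instillations in total (40 days): the drop becomes 0.438. Power is 13% (SD 1.7), 41% (variance proportional to time) or 96% (SD proportional to time).

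**Step 6: unequal windows.** At a constant 2 UTIs per 6 months and no treatment effect, a raw 6-month history of 2 set against an 80-day count of 2 × 0.438 = 0.88 shows a fall of 1.12.

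**The case against.** Four points on the other side have weight.

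- **The 37% figure is not the plan's.** A reader might infer that the plan applies an SD of 1.7 to an 80-day count. It does not: the SD and the drop share the 6-month basis. Pairing a rescaled drop with an unrescaled SD gives a worst-case bound. This stands.
- **The duration is uncertain.** In II.B a session can be read as a day. If each Figure 2 block held 80 such days, the total would come close to 6 months and the stated power would nearly hold. That reading conflicts with III.A and with 80 instillations at 2 per day, but the text does not exclude it, and II.B can also be read as 40 days. The ambiguity is a reason to reconcile the sections. It does not show that the stated power applies.
- **This is called a feasibility study.** Lower power is then tolerable if it is reported. A reader might infer that a null result would be uninterpretable. That goes too far, because an estimate with a confidence interval remains informative at these sample sizes.
- **Nothing says that a 6-month history will be set against a shorter count.** This is correct. Step 6 shows what the undefined windows permit, not what is planned.

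The figures above are also for the single pairwise comparison that the plan powers. The planned between-arm analysis starts with a three-group ANOVA.

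**Conclusion.** The concern holds as a gap in justification. The power arithmetic is sound on its 6-month inputs, but nothing in the documents carries those inputs over to the scheduled window, and the counting windows are not defined. For a drop of 2 per 6 months, 12 per arm gives 69% at 80 days and 74% at 90 days if variance is proportional to time, with bounds of 37% and 96% at 80 days. The stated power survives in full only if the SD shrinks in direct proportion to time. These results assume a drop that is linear in time and the plan's control SD of 0.

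A reader might infer that the mismatch biases the trial. The randomised comparison between arms is not biased by it, provided that all arms are counted over the same windows; what is in doubt is its power. Two other matters are separate and add no weight here. One is the control SD of 0: an SD of 1.7 in both arms gives 79% between-arm power even on the 6-month basis. The other is regression to the mean in the within-arm test.

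**What to change.** 1. Reconcile II.B, III.A and Figure 2 on the length of the intervention, and state whether paused days are made up.
2. Define the pre and post counting windows for symptomatic UTIs, and express both counts in the same person-time unit.
3. Restate the effect, SD and power in II.B.2 for the actual window. Name the SD assumption and show the range around it.

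The cost is revised text in the statistical and timeline sections and, probably, a less favourable stated power. No added participants or visits are needed. For a study described as feasibility, the lower figure can be reported openly.
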